
The Swedish collaborating Institute and the different investigators will however not be directly involved in the volunteer and vaccine studies or in enrollment, recruitment but will support the study by:

- a. Supplying purified colonization factor antigens, rCTB and other purified antigens needed for the ELISA and other immunoassays.
- b. Carrying out quality control of serological assays including quality control of strains from time to time to confirm and when needed.
- c. Transferring new techniques to the ICDDR,B laboratory as and when appropriate.
- d. Working on improvement of ETEC vaccine, in particular increase the amount of CFs on the whole cell components without increasing bacterial numbers.
- e. Giving advice and feedback on latest information and in jointly prepare manuscripts and reports.

Ethical Assurance for Protection of Human Rights

The study will only be initiated after it has been approved by the Research Review Committee (RRC) and the Ethical Review Committee (ERC) of ICDDR,B. In addition, permission from the Directorate of Drug administration of Bangladesh will be obtained for carrying out the ETEC and cholera vaccine studies. We have obtained approval from these committees in our previous studies on patients and vaccinees both related to both ETEC and cholera. We have obtained ethical clearance for ongoing studies on ETEC and cholera patients as well

Principal Investigator: Last, first, middle [name]

as for recruiting volunteers for the CF-BS- ETEC vaccine which was funded by Sida-SAREC (Projects: 96014, 98032) and the USAID funded ETEC Phase II vaccine study in children (Project: 99033). In addition we have obtained similar approval from the ERC for carrying out studies on the WCO1-BS cholera vaccine in adults (Project: 94019, funded by the European Union) or in children (Project: 98001, funded by Thrasher) and for the live oral cholera vaccine Peru 15 (Project:2000-027). In all these studies prior approval was obtained from the ERC.

Before enrollment signed informed consent is obtained from the guardians of the children. The consent form will be written in Bangla in a language and format that is easily understood by the study subject of even little or no educational background. The consent form is read out to the subject or to the guardian/parent of the study subject if he/she is unable to read. Signed consent or the left thumb impression will be obtained from the study subjects or from the parents for participation of the children in the study. Consent will be taken both for participation in the study and for drawing blood and collecting fecal samples. This will be done for the vaccine studies (consent forms in appendix-4a-4c,Part IA).

Risk analysis

The study is planned for a total period of 3 years. Previous studies (from 1993 onwards) mainly carried out by the Sida-SAREC funded projects have led to exchange of technological expertise in the Immunology laboratory such that the planned study will hopefully be carried out without any delay and as planned. We will however be dependent on the supply of CF-BS-ETEC vaccine, the WC-O1-BS vaccine from the Swedish Bacteriological laboratories in Sweden. The study will therefore be dependent on the availability of the relevant vaccines to us at ICDDR,B. The time frame of the study is however planned on the expectation that all the vaccines that will be used in the study will be available from period between 2005-2007 from the Swedish Bacteriological Laboratories.

Use of Animals

Not applicable for ICDDR,B, but needed for Goteborg University.

Dissemination and Use of Findings

The information obtained from this study will help facilitate the Phase III field-testing of the CF-BS-ETEC vaccine. In addition information will be obtained on the immunogenicity of the dried whole cell cholera vaccine which will be helpful in future evaluation of its effectiveness in Bangladesh. The information of the ETEC and cholera vaccine will be helpful for future studies. We hope that this study will lead to a better understanding of the components needed in an ETEC vaccine, the development of protective immunity to ETEC infections and an understanding of the capacity of the inactivated vaccines to elicit a immune response which is appropriate for protection.

References:

Appendix-1

INTERNATIONAL CENTRE FOR DIARRHOEAL DISEASE RESEARCH, BANGLADESH

Studies to enhance and improve immunogenicity of cholera and enterotoxigenic *E. coli* (ETEC) vaccines

Plans for collection of stool and blood from the vaccinees

Sample	Number	Sample collection days	Volume/amount to be collected
Blood (6mo-2 years)	1140 x3=3420	Day 0, 7, 21	1.5 ml for 6 mo to 1 year 3.0 ml for over 1 year
Stool (6mo-2 years)	1140 x3=3420	Day 0, 7, 21	Stool 5 gm

Appendix 2

Studies on the Cholera and ETEC vaccine in children

Age group	Vaccine	No of study subjects*	Timeline
Children (6months -2 years)	1. Cholera vaccine ↓	306	First 6 months
Formulation of vaccine ¹	2. ETEC vaccine	306	
Children (6months -2 years)	1. Cholera vaccine ↓	114	From 6 month to 2 years of initiation of study
Breast Feeding temporary restriction	2. ETEC vaccine	114	
Children (6months-2 years):	1. Cholera vaccine ↓	150	From 6 month to 2 years of initiation of study
Zinc supplementation	2. ETEC vaccine	150	
Total children	Cholera and ETEC	1140	Within 2 years of start of study

¹The first phase of the study will be carried out on the testing of the cholera vaccine in the different buffer formulations and in water. The second phase of this component will be on the ETEC vaccine. After the optimum formulations has been found, it will be used to test the effect of the different interventions, that is zinc and breast feeding on the immunogenicity of the vaccines. The studies on cholera vaccine will be followed by studies on the ETEC vaccine.

For the study, 102 children will be studied in the each of the two buffer components and 102 for the formulation in water; 57 children will be studied in breast feeding; 75 children in the zinc; and for each group in the ETEC vaccine and the cholera vaccine studies. The field component will be completed within the first two years. The laboratory analyses will be carried out as each component has been completed and will continue up to the 3rd year. Data analyses will be carried out as each field and laboratory component has been completed.

Appendix 3

Vaccine dissolving fluid*	Composition of dissolving fluid	Volume to be used for vaccine formulation
Bicarbonate-citric acid buffer, RecipAB ¹	2.0 g NaHCO ₃ , 725 mg citric acid per 100 ml volume in water	20 ml
Rice syrup based electrolyte, CeraVax ²	2 g NaHCO ₃ , 500 mg sodium citrate, 7 g of rice syrup per 150 ml volume in water	20 ml
*Water	Water	20

¹RecipAB is produced by Swedish Bacteriological Laboratories in Sweden. ²CeraVax is produced by Cera Products Inc. Columbia, Maryland. *Groups of children will also be given the vaccine that has been formulated in water to compare the immunogenicity in these participants with those that are receiving the buffered formulations.

Appendix 5a

INTERNATIONAL CENTRE FOR DIARRHOEAL DISEASE RESEARCH BANGLADESH, (ICDDR,B)

Studies to enhance and improve immunogenicity of cholera and enterotoxigenic *E. coli* (ETEC) vaccines:

Screening form

Study Subject ID # Name of the study subject

Basic data

1. Date of interview
DD MM YY
2. Camp colde /Family No. /
3. Screening No. /
4. Study subject's ID /
5. Respondent
1= Mother 2=Father 3= Other
6. Sex
1=Male 2=Female
7. Date of birth
(Bengali/Arabic calendar) DD MM YY
8. Date of birth
(English calendar) DD MM YY
9. Age in years
10. Age in months

[If day is unknown write 15. Month and year must be written. You can write according to Bengali/Arabic calender at the time of interview, and then translate into English later.]

11. Height (cm) .
11. Weight (kg) .
12. % of NCHS (W/A) .
13. % of NCHS (W/H) .
14. Oedema (Present) 1= Yes 2=No
15. Presence of illness 1=No 2=Fever 3= Diarrhoea 4=others

Previous immunization

16. DPT 1=No 2= 1 dose 3=2 dose 4= 3 dose
17. OPV 1=No 2= 1 dose 3=2 dose 4= 3 dose
18. Measles 1=No 2= Yes
19. BCG 1=No 2= Yes

Appendix 5 b

INTERNATIONAL CENTRE FOR DIARRHOEAL DISEASE RESEARCH BANGLADESH, (ICDDR,B)

Studies to enhance and improve immunogenicity of cholera and enterotoxigenic *E. coli* (ETEC) vaccines:

Study subject vaccination and clinical evaluation form

Study child's name | _____ |

Name of the examiner | _____ |

20. Day of vaccination |____| |____|

21. Date |____| |____| |____|
DD MM YY

22. Vaccine lot No. |_____ |

23. Date of vaccination |____| |____| |____|
DD MM YY

24. Type of vaccination |__| 1 = Primary 2 = Secondary

25. Presence of illness

1 = No 2 = Fever 3 = Diarrhoea 4 = Others

General Examination

26. Pulse (rate/min) |____| |____| |____|

27. Respiration (rate/min) |____| |____| |____|

28. Temperature (°C) 1 = Normal 2 = Raised

29. Pallor 1=No 2=mild 3=moderate 4=severe

30. Skin Condition: 1 = Normal 2 = Rash 3 = Others

Systemic Examination

31. Abdominal distension: 1=No 2=Moderate 3=Severe

32. Abdominal tenderness: 1=No 2=Yes if tender 3= localized 4= generalized

33. Lungs(auscultation): 1=Clear 2=Added sound; if added sound 3=Ronchi 4=Rales

34. Heart(auscultation): 1=Normal 2=Added sound

35. Appearance: 1=Normal 2=Irritable 3=Lethargic

36. Movement 1=Normal 2=Restricted

38. Stool test for ETEC 1 = Negative 2 = Positive

39. Blood Sample: . Collection 1 = Yes 2 = No if yes

40. Date of collection |____| |____| |____|
DD MM YY

Appendix 5c

INTERNATIONAL CENTRE FOR DIARRHOEAL DISEASE RESEARCH, BANGLADESH
Studies to enhance and improve immunogenicity of cholera and enterotoxigenic *E. coli* (ETEC) vaccines:
Post vaccination adverse event follow up form
Surveillance After Vaccination

63. Primary vaccination

64. Date
DD MM YY

65. Day 1/ Day 2/ Day 3

66. Completeness of dosing 1 = Yes 2 = No

67. Amount ingested: 1=100% 2= \geq 90% 3= $<$ 90%

LOCAL REACTION (68 - 73)

68. Abdominal pain 1= No 2=Mild 3= moderate 4=severe	69. Distension 1=No 2= moderate 3= severe
70. Vomiting 1=No 2= Yes If yes,	71. Number/day  / day
72. Diarrhoea [$>$ 3] watery or loose stool] 1=No 2= Yes If yes,	73. Number/day  / day

SYSTEMIC REACTION (74 - 81)

74. Fever (Axillary temp $>$ 37.8°C) 1= No 2= Yes	75. If yes, temperature (°C)   .  
76. Loss of appetite/ Poor feeding 1= No 2= Yes	77. Irritability 1= No 2= Yes
78. Nausea 1= No 2= Yes	79. Dizziness 1= No 2= Yes
80. Exanthema 1= No 2= Yes	81. Other 1= No 2= Yes

82. Relation to vaccine: 1 = None 2 = Possible 3 = Probable 4 = Highly probable

83. Therapy required 1= No 2= Yes

84. Outcome 1 = resolved 2 = improved 3 = unchanged 4 = worse

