Sequential progress of the vaccine studies: The vaccine studies will be carried out in a planned and organized manner as has been shown in Appendix 2. Some of the studies will be run in parallel. We hope that by doing this we will be able to maintain a smooth flow and momentum in the study and keep the committees aware of the progress and if necessary make changes as and when thought necessary. In addition this will help us analyze the data and make it available for dissemination, which will be helpful in progressing to Phase III studies of the different components.

Selection of study subjects for vaccine studies:

Healthy children (6 months to 2 years of age) both males and females who have not enrolled in any other research study including that are being conducted by ICDDR,B will be recruited from the urban slums of Mirpur.

Before entering into the study, subjects in the different age groups will be screened from the slums and history recorded and their consent to participate in the study will be obtained (Appendix 4a-4c). We have

previously observed that at least 60% of the families agree to participate in the study. The volunteers prior to enrollment in the study will be carefully examined by a physician. A detailed history of the volunteer of previous immunizations, nutritional status, recent illness (as outlined below) that can compromise the immune system, family background etc. will be taken (Appendix-4a-c). The volunteers should be free from any chronic disease or any recent illness that may compromise the immune system. Children will be excluded from enrollment if interviewers find: (a) a history of chronic gastrointestinal disorder, (b) diarrhoeal illness in the past 2 weeks (diarrhoea being defined as passing of ≥ 3 loose or liquid stools in 24 hours) (c) febrile illness in the preceding week, or (d) other serious chronic illness (e) had antibiotic treatment at least 7 days prior to the enrollment in the study (f) children suffering from third degree of protein energy malnutrition (PEM). The nutritional status of the children to be recruited for the vaccine studies will be monitored using anthropometrical measurements (weight-for-age, and weight-for-length/height). Children below -2SD for weight for height/length of the NCHS median will not be enrolled. Children who have received zinc in the past two months will also not be recruited.

We plan to recruit children in the 6 month -2 year range for immunization.

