Although the study is an open design, the clinician in the field will code the samples before sending them to the laboratory so that the laboratory personnel will be blinded when the analyses are carried out. The laboratory will only know if the samples have to be analyzed for the cholera or the ETEC vaccine immunological responses.

Samples from vaccines that will be collected at 3 time points will be tested for antibody responses. From blood PBMC will be separated for preparation of antibody in lymphocyte supernatants (ALS, Qadri et al. 2003). ALS and serum samples collected from vaccines at the preimmune (day 0) and post-vaccination days (day 7 and day 21) will be tested for antibody responses. ALS and sera from vaccinees receiving the CF-BS-ETEC vaccine or the cholera vaccine will be tested for the IgA antibody responses to different antigens including (for ETEC CFA/I, CS1,CS2,CS3,CS4,CS5, for cholera vaccine to LPS and to CTB for both). Using fecal extracts from the vaccinees at the 3 time-points, IgA antibody responses to CFA/I, V. cholerae O1 LPS and CTB will be measured. These procedures are already set-up in the laboratory of the investigators (Qadri et al. 2000,2003). Further to test the immunogenicity of the cholera vaccine we will test the vibriocidal antibody response at the 3 time points mentioned above as well as the response to LPS (O1 Ogawa and Inaba) using sera. In addition, the IgA and IgG antibody responses to rCTB will be measured in those being immunized with the cholera or the ETEC vaccine. The serum zinc level will also be assessed at the baseline in all the children since it may have an effect on the response to the intervention(s) and the vaccination.

Safety Monitoring Committee

[name] (CSD) will serve as the Chairperson of the committee. Other members include [name].(CSD), [name] (CSD) and [name] (LSD). The members are in no way involved with the project.

Safety endpoint and safety evaluation

The primary end point for evaluating safety will be defined as the occurrence of any of the following diarrhoea, vomiting or abdominal cramps of at least moderate grade. Diarrhea will be defined as three or more loose or liquid stools in any 24-h period. A measured oral or rectal temperature above 38°C will be considered a fever.

Overall laboratory tests for the project

Vaccinees:

Stools will be cultured on MacConkey agar and tested for colonization factors of ETEC by dot blot immunoassay

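### The daily safety form (Appendix 5c, item 72) sets diarrhoea at more than 3 stools, the primary safety endpoint at 3 or more, and exactly-3 days leave no count on the form; the fever definitions also differ

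*Protocol*

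**What the plan says.** **Endpoint.** The Protocol section on safety endpoint and safety evaluation makes the primary safety endpoint "the occurrence of any of the following diarrhoea, vomiting or abdominal cramps of at least moderate grade". It then adds: "Diarrhea will be defined as three or more loose or liquid stools in any 24-h period". The exclusion criteria, under selection of study subjects, use the same cut-off of at least 3 "loose or liquid stools in 24 hours".

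**Daily form.** Appendix 5c is the form for days 1 to 3 after vaccination. Item 72 is a yes/no item on more than 3 "watery or loose stool"; in the text available it reads "Diarrhoea [$>$ 3] watery or loose stool] 1=No 2= Yes If yes". The stool number per day (item 73) follows that condition.

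**Fever.** The safety section sets fever as "A measured oral or rectal temperature above" 38°C. Item 74 of Appendix 5c reads "Fever (Axillary temp" above 37.8°C, and the temperature itself (item 75) is entered only after a yes.

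**Other form.** Appendix 5d asks for every adverse event, one per line, with severity and free text. It has no stool-count field and states no diarrhoea threshold.

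**The concern.** The form and the endpoint differ by one stool, at the boundary of the definition. The count that could settle the matter later is taken only from children who have already passed the stricter threshold. If the form is completed as printed, the diarrhoea component is under-counted, and an analysis plan cannot repair this from form 5c because the number was never written down.

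The protocol chose daily home visits as an added precaution in children aged 6 months to 2 years, its background reports some reactogenicity of the ETEC vaccine below 17 months, and the data analysis section plans to compare adverse reaction rates. The rates compared should follow the stated definition. The same applies to fever, which the text and the form define by different measurement sites and thresholds.

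**Working it through.** The documents give no safety rate, safety sample size or safety power, so there is no figure of the plan to reproduce. The check is a side-by-side reading, followed by a bound and an illustration.

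**1. What happens to each daily count**

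| Loose stools in the day | Endpoint text (3 or more) | Item 72 as printed (more than 3) | Item 73 |
|---|---|---|---|
| 0 to 2 | not diarrhoea | No | blank |
| exactly 3 | diarrhoea | No | blank |
| 4 or more | diarrhoea | Yes | number recorded |

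The text and the form disagree only in the middle row. On form 5c that row looks the same as the top row, so it cannot be rebuilt.

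**2. Is the symbol right?** In the available text item 72 has one opening and two closing brackets, so the cell is damaged and a misread sign is possible. Against that, item 67 on the same form keeps the at-least sign: "67. Amount ingested: 1=100% 2= \geq 90% 3= $<$ 90". The two signs are therefore told apart on this form. More than 3 is the likelier reading but is not certain.

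**3. Fever**

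| | Safety section | Appendix 5c, item 74 |
|---|---|---|
| Site | oral or rectal | axillary |
| Threshold | above 38°C | above 37.8°C |

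The site is given in words, so this mismatch does not depend on any symbol. The form asks for no oral or rectal reading, so the text definition cannot be applied to form 5c data.

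**4. Ceiling on exposure.** Inputs: home visits on 3 days after each dose and 2 doses (overall design section); 1140 children (Appendix 2).

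3 × 2 × 1140 = 6840 surveillance child-days at most.

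This is the denominator, not a number of lost events.

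**5. Illustration only.** The share of qualifying days that have exactly 3 stools is P(X = 3) / P(X ≥ 3) = [P(X ≥ 3) − P(X ≥ 4)] / P(X ≥ 3). The distribution of the daily count X is assumed; none is given in the documents.

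| Assumed mean per day | Poisson: P(X≥3), P(X≥4) | Share exactly 3 | Negative binomial, k = 0.5: P(X≥3), P(X≥4) | Share exactly 3 |
|---|---|---|---|---|
| 0.5 | 0.0144, 0.0018 | 88% | 0.0498, 0.0222 | 55% |
| 1 | 0.0803, 0.0190 | 76% | 0.1340, 0.0805 | 40% |
| 2 | 0.3233, 0.1429 | 56% | 0.2666, 0.1950 | 27% |
| 3 | 0.5768, 0.3528 | 39% | 0.3559, 0.2815 | 21% |

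For example, Poisson with mean 1: (0.0803 − 0.0190) / 0.0803 = 0.76. (Shares use unrounded probabilities.) The range of 21% to 88% is too wide to serve as an estimate. It shows only that the boundary category need not be small. It refers to days that meet the diarrhoea definition, not to children and not to the composite endpoint.

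**The case against.** The strongest reply is that the symbol is unproven. The cell is damaged at the disputed place, both text definitions say 3 or more, and a correct sign in item 67 does not prove a correct reading of item 72. That stands as a reason to check the original page. If the page shows an at-least sign, the diarrhoea mismatch disappears; the fever mismatch remains.

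A reader might also infer that the primary safety endpoint as a whole cannot be recovered. The documents do not support that:

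- The endpoint is a composite. Form 5c still records vomiting with its number per day, graded abdominal pain, and every day with 4 or more stools. A child with 3 stools may qualify through another component.
- Appendix 5d can hold a 3-stool episode, with a severity grade. The endpoint sentence can be read as requiring at least moderate grade for all three symptoms. On that reading 5d matters more, because 5c grades neither diarrhoea nor vomiting. Capture on 5d is still not assured, since nothing there prompts for the stool number or states the cut-off.

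A reader might likewise take 6840 as days lost. It is every scheduled surveillance day.

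On fever, it is fair to say that fever is not part of the primary safety endpoint, and that axillary values above 38°C can be picked out from item 75. That aligns the number but not the site.

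**Conclusion.** The point holds in a limited form. As printed, item 72 contradicts the diarrhoea definition of the primary safety endpoint. Because the count depends on a yes, days with exactly 3 loose stools are missed on form 5c and cannot be restored from it. Other components and higher stool counts are unaffected, and some of the missed episodes may reach Appendix 5d. The share of events missed cannot be stated from the documents.

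The diarrhoea part assumes that the printed sign is more than, which is likely but unconfirmed, and that staff follow the form literally. The fever part needs no assumption about a symbol: site and threshold both differ between text and form. Sample sizes and immunogenicity conclusions are not touched, because the group sizes rest on immune responses. The correction should be made before the forms are used, since data not recorded at the visit cannot be added later.

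**What to change.** 1. Check the sign in item 72 on the original page.
2. Reconcile item 72 with the diarrhoea definition in the safety section, so that text and form carry one threshold.
3. Take the condition off item 73: record the number of loose stools, including zero, for every child on every surveillance day, whatever the answer to item 72. The definition can then be applied in analysis whichever sign the page shows.
4. Reconcile the fever site and threshold between the safety section and item 74. Which definition to keep is for the investigators.

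The cost is a few edits to one form and, if needed, one sentence of the protocol. No visits or samples are added; staff enter one extra number at home visits that are already planned.

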Appendix 5d

INTERNATIONAL CENTRE FOR DIARRHOEAL DISEASE RESEARCH, BANGLADESH
 Studies to enhance and improve immunogenicity of cholera and enterotoxigenic *E. coli* (ETEC) vaccines
adverse event form
Surveillance After Vaccination

Random # **Investigator** **Initials of participants** **Inpatient**
Number

Were there any adverse events associated with administration, whether or not they were considered vaccine-related?
 If yes, please complete all sections below (circle appropriate number) 1=No & 2=Yes.

Adverse events, specify: Please list one event per line	Serious Including Life-threat 1=No 2=Yes	Start Date		Stop Date		Severity 1=Mild 2=Moderate 3=Severe	Relation to Study Vaccine 1=None 2=Remote 3=Possible 4=Probable	Therapy Required 1=No 2=Yes (specify below) 5=Highly Probable	Outcome 1=Resolved 2=Improved 3=Unchanged 4=worsened 5=Follow up not done
		dd	mm	yy	dd				
	1 2					1 2 3	1 2 3 4 5	1 2	1 2 3 4 5
	1 2					1 2 3	1 2 3 4 5	1 2	1 2 3 4 5
	1 2					1 2 3	1 2 3 4 5	1 2	1 2 3 4 5

Further details of adverse events and classification of above entries (specify dates and include information on concomitant medications and concurrent conditions)

--

Date.....

Investigator's signature.....

